NATIONAL POLYTECHNIC INSTITUTE

School of Medicine

SECTION OF GRADUATE STUDIES AND RESEARCH

“Gene modulation of NLRP3, IL-1 β and TNF- α in peripheral blood of patients with exogenous obesity treated with Berberine.”

Principal Clinical Research

PhD [name]
PhD [name]

Clinical sub-investigator

PhD [name]
Nutritionist [name]

ESM CE-01/7-12-2015

Mexico City, 15 August 2015

ABSTRACT

Background: In the treatment of exogenous obesity more than 800 traditional plants are used, such is the case of *Berberine* a phytopharmaceutical. This phytodrug has been shown to be anti-obesogenic in the Asian population, however its effect on our population is unknown. **Objective:** To determine the effects of *Berberine* on the gene modulation of NLRP3, IL-1 β and TNF- α in peripheral blood of patients with exogenous obesity. 120 patients were studied, treated with: hypocaloric nutritional plan, hypocaloric nutritional plan and moderate aerobic exercise, hypocaloric nutritional plan, moderate aerobic exercise plus *Berberine* and finally a normo-weight group without treatment. Anthropometric measurements, biochemical tests, clinical and gene expression data of NLRP3, IL-1 β and TNF- α were obtained. The anthropometric measurements, the treatment with *Berberina* obtained, with the exception of ICC, statistically significant results, while in the biochemical results the groups 2 and 3 showed similar results, those treated with Berberina only the VLDL

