What is the effect of Berberine on the gene expression of IL-1 β , TNF- α and NLRP3, in peripheral blood cells in individuals with exogenous obesity?

9. Objectives

General objective:

To determine the effects of Berberine on gene expression of cytokines IL-1 β , TNF- α and NLRP3 in individuals with exogenous obesity.

Specific Objectives:

1. To form groups diagnosed with exogenous obesity.
2. To evaluate anthropometric parameters
3. To evaluate biochemical parameters
4. To quantify the expression (mRNA) of NLRP3, IL-1 β and TNF- α
5. To establish the differences in gene expression between individuals with exogenous obesity and control subjects.

10. Hypothesis

Berberine inhibits gene expression of NLRP3, IL-1 β and TNF- α in individuals with exogenous obesity.

11. Material and methods

Type of study:

An experimental, analytical, longitudinal, prospective study of comparative groups was carried out.

Study subjects

Ninety patients with type I and II obesity will be selected, as well as 30 control subjects (healthy adults), who agreed to be donors of a peripheral blood sample, 2 tubes (1: biochemistry, 2: gene expression) channeled to the Obesity Program unit (Comprehensive Medical Service, ESM, IPN), with the following selection criteria.

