12.1. Selection criteria

Inclusion

Human peripheral blood obtained from adult donors with the following characteristics:

- Patients with $\text{BMI} \geq 30\text{kg/m}^2$
- With risk factors for type 2 diabetes (history of diabetic parents or siblings, sedentary habits)
- Fasting blood glucose $\leq 126 \text{ mg/dL}$ or glycosylated hemoglobin $< 6.5\%$
- Controlled arterial hypertension
- >18 years of age
- Accept and sign the informed consent

No inclusion

- Hypersensitivity to the components of the formula
- History of hypoglycemic episodes
- History of obesity of endogenous origin
- History of serious psychological, psychiatric, eating or neurological disorders

- History of hyperthyroidism, heart disease, diabetes, liver or kidney failure, glaucoma, epilepsy
- Pregnancy or lactation

Exclusion criteria

- Pregnancy
- Diabetics
- Presenting any serious adverse effect
- Patients who decide to withdraw from the protocol

Elimination

- Samples contaminated during processing
- Lysed blood samples
- Coagulated blood simple.

Variable Description

Independent Variable

Berberine

Category: quantitative.

Measurement scale: ratio.

Measurement unit: 500 mg with excipient q.s.

Operational definition: the tested dose of Berberine was 500 mg, given to patients for 3 months.

Dependent

Gene expression of IL-1 β , TNF- α and NLRP3.

Category: quantitative.

Measurement scale: discrete, continuous.

Measurement unit: arbitrary units.

Operational definition: Cytokines were determined with commercial qPCR equipment/reagents, and their arbitrary units/relative expression were determined by a specific standard curve for each one.

Observation method: open.

Sampling method: non-probabilistic sampling of consecutive comparative groups that met the selection criteria, until reaching the sample size that constituted the study groups (patients with exogenous obesity).

Operational description of the study: Berberine has been provided by the Medix laboratory, in 500 mg capsules, to treat patients for 3 months.

Study groups

The individuals will be distributed into four groups:

- Group 1. Individuals with exogenous obesity: nutritional plan intervention for lifestyle change.
- Group 2. Individuals with exogenous obesity: nutritional plan intervention, moderate controlled aerobic exercise for lifestyle change.

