- Group 3. Individuals with exogenous obesity: nutritional plan intervention, moderate aerobic exercise and Berberine phytopharmaceutical. With biweekly sessions for 3 months.
- Group 4. Normal-weight individuals without intervention.

Blood samples were taken after informed consent from the participants, they were informed of the intervention and the group to which they belonged, they were also taken at the end of the study.

Procedure

In the selection, obtaining information, anthropometry and blood biochemistry, the subjects of the study will be asked for authorization and their participation will be requested after a detailed explanation of the risks and benefits of the protocol, obtaining signed informed consent.

Obtaining the samples

The universe of the study will be individuals from 19 to 55 years of age with exogenous obesity; they will be recruited in the Obesity Projects area of the Postgraduate Studies and Research section of the Higher School of Medicine of the National Polytechnic Institute, referred by the Comprehensive Medical Service.

Each participant will be asked in writing to enter the study, each one was identified, and a clinical history was prepared with anthropometric measurements: weight, percentage of body fat, percentage of visceral fat, height, BMI. Peripheral blood will also be taken for blood biochemistry and messenger RNA extraction and qPCR tests to determine gene expression of NLRP3, IL-1 β and TNF- α .

Biochemical tests.

Peripheral blood samples will be evaluated by an external laboratory.

Blood samples will be collected at the beginning and three months after treatment. Participants were called at 7 am, after fasting for at least 8 hours, and the sample was collected in Vacutainer tubes (BD, USA), added with ethylenediaminetetraacetic acid (EDTA) to prevent coagulation. 4 mL of blood was taken from everyone; from there, 1 mL of Trizol (Sigma-Aldrich, USA) was added to 2 2 mL tubes with 100 μ L per tube. The blood was vortexed for 30 s and stored at -70 °C until processing. The rest of the blood was stored at -20 °C.

Anthropometric evaluation

The somatometry of each participant will be determined by wearing light clothing and without shoes: weight, height, % body fat, % visceral fat.

Height

It will be defined as the distance between the vertex and the support plane.

- Instrument: Stadiometer (Seca mod. 208).
- The measurement will be expressed in cm with a precision of 1 mm.

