“Low-calorie” Mediterranean diet: This is the model supported by SEEDO because it represents this balanced and healthy approach, with a low intake of saturated and trans fatty acids and added sugars, and a high consumption of vegetable fiber and monounsaturated fatty acids. Its health benefits, including mortality, are clearly established in the literature.

High-protein diet: Based on the satiating effect and less loss of lean mass. The intake is increased to >1.2 g/kg/day, with a minimum intake of 90 g daily.

Nutritional Management

The nutritional management plan in this project will be aimed at improving the lifestyle and quality of life of patients, as well as reducing their body weight. This intervention will be done according to the nutritional management for obesity developed by nutritionists from INCMNSZ.

The goals of the nutritional plan were to establish healthy eating habits with a 10-15% reduction in body weight during treatment.

Nutritional Consultations

The consultations will be biweekly to evaluate body weight, anthropometry and adherence to the nutritional regimen, in addition to monitoring the modification of eating habits.

Clinical-nutritional history

In this clinical history, the lifestyle of the patients will be evaluated, the activities from the time they will wake up until bedtime will be questioned, their physical activities, allergies or intolerances, eating habits such as: meal times, tastes, preferences, quantities, type of food preparation, economic amount allocated, places of food, if they ate with electronic distractions, among others, to know the needs of each participant and adequately prescribe the food plan.

Food frequency

A food frequency survey from ENSANUT 2012 will be applied to learn about eating habits and determine the consumption of energy, important macro and micronutrients. The same survey analyzes and reports the results when capturing the data. With the evaluation of the diet and the anthropometric, biochemical, clinical, dietary and economic indicators, a nutritional diagnosis and the degree of obesity of each patient were established.

Energy expenditure

After the diagnosis, the prescription of the individualized food plan was prepared. The basal energy expenditure (BEE) was calculated with the Harris Benedict formula, and the current body weight.

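### Serious adverse effects and withdrawal are post-entry exclusions, with no rule keeping those patients in follow-up, analysis or safety results; followed as written, blood outcomes are compared in completers only.

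*Combined protocol and SAP*

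**What the plan says.** Section 12.1 has three separate lists. *No inclusion* bars people at entry; pregnancy and a history of diabetes are on it. *Elimination* concerns only contaminated, lysed or clotted blood samples. Between them, *Exclusion criteria* names pregnancy, diabetics, "Presenting any serious adverse effect" and "Patients who decide to withdraw from the protocol".

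Other text that bears on the point:

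- **Design.** The same section gives "Observation method: open" and consecutive sampling "until reaching the sample size that constituted the study groups". It does not say whether excluded patients are replaced.
- **Numbers.** Study subjects: "Ninety patients with type I and II obesity will be selected", plus 30 controls. Abstract: "120 patients were studied".
- **Blood outcomes.** Biochemical tests: "Blood samples will be collected at the beginning and three months after treatment".
- **Anthropometry.** Nutritional Consultations: "The consultations will be biweekly to evaluate body weight, anthropometry and adherence to the nutritional regimen". The later Anthropometric Evaluation section also has measurements every 15 days.
- **Harms.** The Adverse effects log has patients record events for reporting. It gives no denominator or summary and does not mention patients who have been excluded.
- **Analysis.** The Statistical analysis section gives means with SE, ANOVA, Student's t test and a 0.05 threshold. It defines no analysis set, missing-data rule or safety analysis.

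**The concern.** A serious adverse effect of the intervention and a decision to withdraw can arise only once a patient is in the study. Excluding patients on these grounds selects the analysed sample on events that the interventions may influence. Group 3 differs from Group 2 by berberine, and participants know their group, so the number and type of patients leaving may differ between the two. If leaving also relates to response, the Group 3 v Group 2 contrast mixes any berberine effect with the effect of who stayed.

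Gene expression, the subject of the general objective, is the most exposed outcome: a patient removed without a 3-month sample has no follow-up value at all. Anthropometry is less exposed because interim values exist, but no rule says they are used. For harms, the patients removed include those whose events matter most to a safety summary.

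**Working it through.** **1. What the lists do.** Entry ineligibility and sample quality each have their own list. Pregnancy is on both the entry list and the exclusion list, and two of the exclusion items cannot occur before entry. Reading the exclusion list as removal after entry is therefore the natural reading. No section restores these patients to follow-up, analysis or safety counts.

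**2. What can be reproduced.** The documents give no dropout rate, effect size, SD or sample-size calculation. The only check is 90 + 30 = 120, which agrees with the Abstract.

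**3. Illustration of the efficacy bias.** Every input here is assumed: 90/3 = 30 per obesity group, SD 1, lower values better, no true effect, poorer responders leaving, no replacement, two-sided test at 0.05. Let r be the correlation of the outcome with a latent leaving score, where the fraction q with the highest scores leave. In large samples the completer mean shifts by −r·φ(z)/(1−q), where z is the upper-q normal quantile.

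- q = 20%: φ(z) = 0.280, and 0.280/0.8 = 0.350.
- q = 10%: φ(z) = 0.1755, and 0.1755/0.9 = 0.195.
- 20% v 10%: −r(0.350 − 0.195) = −0.155r, which is −0.039 at r = 0.25 and −0.077 at r = 0.5.
- 20% v 0%: −0.350r, which is −0.087 at r = 0.25 and −0.175 at r = 0.5.

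Simulation of 40,000 trials per case, with exactly 3 or 6 of 30 leaving where loss is 10% or 20%, gives:

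| Loss, Group 3 v Group 2 | r = 0.25: bias (SD), type I error | r = 0.5: bias (SD), type I error |
|---|---|---|
| 20% v 20% | 0.00, 5.1% | 0.00, 5.7% |
| 20% v 10% | −0.04, 5.3% | −0.08, 6.7% |
| 20% v 0% | −0.08, 6.2% | −0.17, 9.9% |

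Negative favours berberine. Reversing the losses at r = 0.5 gives +0.07 SD (10% v 20%) and +0.17 SD (0% v 20%). The 5.7% under balanced loss is not bias. It comes from applying an ordinary t test after a fixed number have been removed by rank, so a little of the 6.7% and 9.9% has the same source.

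r is not the correlation of outcome with leaving itself. At 20% loss and r = 0.5 that correlation is 0.5 × 0.280/√(0.2 × 0.8) = 0.35. If it were 0.5, 20% v 0% would give a bias of 0.5 × √(0.2/0.8) = 0.25 SD.

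**4. Safety.** One serious event in 30 is 3.3% (exact 95% CI 0.1 to 17.2). If that patient is removed, the group reads 0/29.

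**The case against.** The strongest reply is that the documents show no harm done. No loss is reported, the number studied equals the number planned, and an adverse effects log exists. All of that is true. A reader might infer from the equality at 120 that leavers were replaced or left uncounted. The documents do not support this, because the same total fits no losses, replacement, or counting at enrolment.

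A reader might also infer that harm must be understated. That goes too far. The log may be reported in full. If it is not, omission lowers the serious-event rate within a group, but the rule covers every group, so harm in Group 3 relative to another group could be distorted either way.

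Three further objections stand in part:

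- *Diabetics* may only catch ineligibility shown by the baseline sample. Removing those patients on baseline information is not selection on outcome.
- Body-composition values after a pregnancy begins need a stated rule, not automatic inclusion.
- Withdrawal from the protocol may end consent to blood sampling, which is distinct from consent to use data already held.

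Finally, no randomisation is described and the plan does not name Group 3 v Group 2 as primary. Keeping patients in the group they entered therefore does not restore a randomised comparison. None of this supplies the missing rule.

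**Conclusion.** The point holds as a gap in the analysis set and in reporting. The text states a post-entry removal rule, and following it yields a completers-only comparison for gene expression and biochemistry. A reader might infer that the results therefore favour berberine. The documents do not show this: the sign of the bias depends on who leaves which group, and balanced loss under the same mechanism gives none.

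Under the assumed losses the bias runs from 0 to about 0.17 SD in either direction, with type I error up to about 10% in the most unbalanced case and near 5% to 6% in the weaker ones. These figures show scale only and do not estimate what happened in this study. The within-group safety effect needs no dropout assumption, only that excluded patients' events are left out. The plan does not prevent that, but does not require it either. The change is worth making because it costs little; the size of the bias is not established.

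**What to change.** Leave the clinical stopping criteria unchanged, and state separately what happens to the data.

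- **Analysis set.** Keep patients with a serious adverse effect, or who stop early, in the group they entered.
- **Data.** Seek the 3-month sample and anthropometry only from those who still consent to those procedures. Use data already collected, including biweekly anthropometry, unless consent for data use is withdrawn.
- **Method.** Analyse all available data adjusted for baseline, with completers as a sensitivity analysis. State that baseline adjustment alone is not enough: at 20% v 0% and r = 0.5 it leaves −0.154, −0.128 or −0.090 SD for baseline-outcome correlations of 0.3, 0.5 or 0.7. Obtaining half, 80% or all of the leavers' samples brings the unadjusted bias to −0.075, −0.028 or 0.001 SD.
- **Special cases.** Treat ineligibility shown by the baseline sample, such as diabetes, as a baseline exclusion. State in advance how body-composition values after a pregnancy begins are handled.
- **Reporting.** Give losses, reasons and replacements by group, say whether the 90 counts enrolled or completed patients, and report adverse events for everyone who started an intervention.

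The cost is protocol wording and a few follow-up contacts. The estimated effect may be diluted, and power falls where samples cannot be obtained: for an assumed effect of 0.74 SD, from 80% with 30 v 30 to 73% with 24 v 27. The change addresses post-entry selection only, not baseline differences between groups. If the study has ended, as the Abstract's past tense suggests, new samples may be out of reach, but the analysis and reporting items still apply.

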The thermocycler was programmed with the following scheme: preincubation for one cycle of 10 minutes at 95°C; the reaction for 45 consecutive cycles (denaturation at 95°C for 10 seconds, annealing at 60°C for 30 seconds and extension at 72°C for 1 second) and the final incubation at 40°C for 30 seconds.

Table 5. Oligonucleotide sequences used to determine gene expression.

Gen	Proteins	Sequences	Concentration
NLRP3	Proteína 3 que contiene dominios NACHT, LRR y PY	F: 5' GCA AGA CTT TGA CAA CAT GC3' R: 3'CAC CTG TTG TGC AAT CTG AAG5'	10nM
TNF- α	Factor de necrosis tumoral alfa	F: 5' CAGCCTCTCTCCCTTGAT3' R: 3'GCCAGAGGGCTGATTAGAGA5'	10nM
IL-1 β	Interleucina 1 beta	F: 5' TTG GGT AAT TTT TGG GAT CTT AC3' R: 3'CTG TCC TGC GTG TTG AAA GA5'	10nM
B-actina	Gen constitutivo	F: 5' AGC CAC ATC GCT CAG ACA C3' R: 3'GCC CAA TAC GAC CAA ATC C5'	10nM

Statistical analysis

The values of each determination are expressed as the mean \pm SE. The differences between the groups were calculated with ANOVA. Differences between the groups will be determined by using Student's T test. In all tests, a value less than or equal to 0.05 was considered significant.

Ethical aspects

The study will be of lower than minimum risk, since no blood was obtained from the participants in quantities greater than the limit established by the Regulations for Research on Human Beings of the General Health Law. The project was evaluated,

approved and accepted by the Research and Ethics Committee of the Higher School of Medicine of the National Polytechnic Institute.

The study was carried out in accordance with the ethical principles:

- Declaration of Helsinki of the WMA - Ethical principles for medical research involving human beings¹²⁶.
- Written and signed informed consent as stipulated in article 21 of the General Health Regulations on Health Research¹²⁷.
- As stipulated in article 17 of the General Health Regulations on Health Research, this project is classified as minimal risk¹²⁷.
- The protocol was carried out in compliance with the recommendations established in NOM-087-ECOL-SSA1-2002, which addresses matters related to Environmental Protection and Environmental Health; Biological-infectious Hazardous Waste¹²⁸.

Material Resources

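### No random or concealed allocation of the 90 obese patients is described and the planned tests have no baseline term, so a Group 3 versus Group 2 difference cannot be attributed to berberine unless allocation is shown to be random

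*Combined protocol and SAP*

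**What the plan says.** The general objective is "To determine the effects of Berberine on gene expression of cytokines" IL-1β, TNF-α and NLRP3 in people with exogenous obesity, and the hypothesis is that berberine inhibits their expression. Under Type of study the design reads: "An experimental, analytical, longitudinal, prospective study of comparative groups was carried out". Randomised is not among the descriptors.

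Under Study subjects there are 90 obese patients and 30 controls. The sampling method, under Variable Description, is non-probabilistic: consecutive comparative groups meeting the criteria, taken until the sample size is reached. The same part states "Observation method: open". Under Study groups, "The individuals will be distributed into four groups":

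- Group 1: nutritional plan.
- Group 2: nutritional plan and moderate aerobic exercise.
- Group 3: nutritional plan, moderate aerobic exercise and berberine.
- Group 4: normal-weight people without intervention.

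The text after this list says of participants that "they were informed of the intervention and the group to which they belonged". No placebo is described.

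Under Biochemical tests, "Blood samples will be collected at the beginning and three months after treatment". Under Statistical analysis, "The differences between the groups were calculated with ANOVA"; Student's t test is also named for differences between groups, with significance at 0.05 or below. That section does not say whether final values or changes are compared, and it names no covariate and no specific contrast.

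**The concern.** Groups 2 and 3 are the only pair meant to differ by berberine. Group 1 lacks the exercise component, and Group 4 is normal-weight and untreated. Any test of the berberine hypothesis therefore rests on Group 3 versus Group 2, although the plan never names that contrast and specific objective 5 compares obese individuals with controls.

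A difference between these two groups is evidence of a drug effect only if patients entered them by a process unrelated to prognosis. The protocol's own background section on adipose tissue and inflammation relates these markers to body fat and body weight. A difference in adiposity between the groups at entry is thus a confounding route that the document itself recognises. With no described allocation method and no baseline term in the analysis, the plan as written would report such a difference as an effect of berberine.

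**Working it through.** **1. Allocation text.** The methods contain no random sequence, ratio, concealment, matching or stratification for Groups 1 to 3. In the methods the word random occurs only in the name of a PCR reagent. The sampling sentence describes recruitment. It may hint that groups were filled one after another, but it does not say so.

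**2. Sample size.** The only design figure that can be reproduced is the total: 90 + 30 = 120, which agrees with the abstract. No power, SD, effect size or split of the 90 is given.

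**3. How much a baseline gap could matter (illustration only).** The documents give none of these inputs except the 0.05 level. Assumed: 90/3 = 30 per group, a two-sided test, no berberine effect, baseline-to-three-month correlation r, and a baseline gap g (in SD units) between Groups 2 and 3. The SE of a difference in means is √(2/30) = 0.258 SD. For each t test the noncentrality is the expected difference divided by its SE, with 58 degrees of freedom.

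- Final values, gap shrinks by r: rg/0.258. With r = 0.5 and g = 0.5, 0.25/0.258 = 0.97, rejection 15.9%.
- Final values, gap persists: g/0.258 = 0.5/0.258 = 1.94, rejection 47.8%.
- Change scores, gap shrinks: (1 − r)g / √(2(1 − r) × 2/30). With r = 0.5 this is again 0.25/0.258 = 0.97, rejection 15.9%.
- Change scores, gap persists: noncentrality 0, rejection 5%.
- ANCOVA on baseline, by simulation: about 5% if the gap shrinks, about 18% if it persists.

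| Gap g, r | Behaviour of gap | Final values | Change | ANCOVA |
|---|---|---|---|---|
| 0.5 SD, 0.5 | shrinks | 16% | 16% | 5% |
| 0.5 SD, 0.5 | persists | 48% | 5% | 18% |
| 0.25 SD, 0.5 | shrinks | 8% | 8% | 5% |
| 0.25 SD, 0.5 | persists | 16% | 5% | 8% |
| none (randomised), 0.5 | – | 5% | 5% | 5% |

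For g = 0.5 SD and r from 0.3 to 0.7: with a shrinking gap, final values run from 9% to 27% and changes from 20% down to 11%; with a persisting gap, ANCOVA runs from 27% down to 12%.

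**4. Reading.** ANCOVA is right if the gap shrinks and change scores are right if it persists. No single analysis protects against both, so adjustment does not replace randomisation.

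**The case against.** The strongest reply is that only an omission is shown. The text is translated, calls the study experimental, and nowhere says that allocation was non-random. That stands: a reader might infer that the study was non-randomised or that the groups were unbalanced, and the documents support neither. But experimental does not mean randomised, and the omission alone leaves the causal claim without a stated basis.

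A reader might also infer from the sampling sentence that the groups were filled in turn, so that calendar time is confounded with treatment. The wording allows this but does not establish it. Likewise, the sentence on telling participants their group might be read as disclosure before consent or baseline sampling. It places the blood samples after consent but leaves the order of disclosure ambiguous, so nothing here rests on it.

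The illustration can fairly be called generic: every rate above 5% comes from an assumed gap, and 0.5 SD is about 1.9 chance SEs (0.5/0.258). It shows a mechanism and does not measure this trial. That Group 3 versus Group 2 is not named in the plan is also true, but no other pair can address the hypothesis.

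Finally, randomisation would not remove everything. The study is open with no placebo described, so even a randomised comparison would estimate the effect of adding open-label berberine.

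**Conclusion.** The point holds as a gap in the plan, not as proof of bias. No random or concealed allocation of the 90 obese patients is described, and the planned tests use no baseline term although baseline samples are taken. Until allocation is shown to be random, a Group 3 versus Group 2 difference cannot be attributed to berberine.

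The size of any bias is unknown. Under the assumptions above, the false-positive rate of the unadjusted test on final values would be about 16% to 48% instead of 5%. The conclusion does not depend on those figures, because the missing allocation statement is enough. It must be resolved before the causal objective can be interpreted.

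**What to change.** **If the study is complete**, as the abstract suggests ("120 patients were studied"):

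- State how patients were allocated to Groups 1 to 3.
- Name Group 3 versus Group 2 as the contrast for the berberine hypothesis.
- For each of the three genes, replace the unadjusted test by ANCOVA of three-month log relative expression on baseline log relative expression, with a stated multiplicity rule across the genes.
- Unless allocation was random, call the study non-randomised, add baseline BMI, age and sex as covariates, and show a change-score analysis alongside. Say that the two analyses make different assumptions about the baseline gap, that a conclusion that differs between them is not robust, and that unmeasured confounding remains. Report association, not effect.
- Report calendar-time confounding only if the groups were in fact filled consecutively.

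**If patients are still to be enrolled:** randomise the same 90 patients 1:1:1 to Groups 1 to 3 from a list concealed until consent and baseline sampling are complete. Keep Group 4 as a non-randomised reference and use the same ANCOVA and multiplicity rule.

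**In either case**, state that the comparison is open with no placebo described, so it estimates the effect (or association) of adding open-label berberine.

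**Cost.** For a completed study: a paragraph on allocation, reanalysis of data already collected and more cautious wording. For an enrolling study: a protocol amendment and a concealed list, with the same patients, visits and assays; some patients may decline their assigned group.
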